## 5 STUDY ASSESSMENTS

PROs were assessed with study Subjects. Sarecycline treatment effectiveness was assessed by treating Site Investigator using IGA scores. Safety associated with sarecycline was evaluated in terms of adverse events and ADRs during the treatment period.

### 5.1 PRO Assessments

A combination of a validated questionnaire and an ad hoc questionnaire prepared via modified delphi panel consensus method involving dermatologists, were used for PRO assessments.

#### ASIS Questionnaire:

The ASIS is a 17-item questionnaire that asks patients about the signs and impact of AV (Appendix B); responses are reported as two scales: Signs (9 items), and Impact (8 items). Impact domain has two subscales, pertinent to Emotional (6 items) and Social impact (2 items). The following questions (items) correspond to each scale:

Scale	Items
Signs	1-9
Impact	10-17

All items are scored on a five-point adjectival response scale, with a potential score of 0 to 4, even though the individual item responses are different for certain question clusters. A domain score is determined by the average of scores in each scale within the domain. A total score is the average of all 17 items. Higher scores on the ASIS Sign domain, comprised of all items that assess symptoms (items 1-9), indicate the presence of more severe symptoms, whereas higher scores on the ASIS Impact domain, comprised of all of the items that assess impacts (items 10-17), indicate a greater negative impact of acne on HRQoL and appearance. The questionnaire was administered in entirety, at baseline and at Week 12 post-index date.

At Weeks 4 & 8 post-index date, Subjects were asked to complete ASIS Item # 9 (how is your acne on your face right now) and ASIS Item # 10 (rate how your face looked because of your acne).

#### Expert Panel Questionnaire (EPQ):

Ten (10) ad hoc questions related to patient perception of impact of Acne on their social functioning, emotional functioning and activities of daily living were formulated based on an expert consensus involving a panel of dermatologists using modified delphi method. The items relate to how Acne impact patient's mood (anger), social interactions, general thoughts/worries about Acne and one's future goals, and impact on daily activities, including sleep (Appendix B).

All items are scored on a five-point adjectival response scale, with a potential score of 0 to 4, even though the individual item responses are different for certain question clusters. The questions were administered in entirety, at baseline and at Week 12 post-index date.

### **5.2 Treatment Satisfaction Assessments**

Investigator's global satisfaction with sarecycline treatment was assessed at Week 12 using a single question: "how satisfied are you with sarecycline treatment outcomes", with response options ranging from 'Very Satisfied' to 'Very Dissatisfied'.

### **5.3 Treatment Effectiveness Assessments**

The effectiveness of sarecycline treatment was assessed from the perspective of Site Investigators as well the Subjects.

#### **5.3.1 *Investigator Assessments***

An IGA scale of 0 (Clear) to 4 (Severe) was used by the Site Investigators to assess the severity of a subject's facial acne at the time of study encounters. The IGA is representative of the investigator's overall general assessment of the subject's Acne and takes into account the quality, as well as the quantity, of lesions. These assessments were done at baseline encounter to document AV severity before initiation of sarecycline treatment; the assessments were repeated by the Site Investigators at study subject follow-up encounters at Weeks 4, 8 & 12, post-index

date. The comparison of follow-up assessments to the baseline assessment will help determine treatment effectiveness. All Investigator assessments were conducted via in-person visits/encounters at baseline and week-12. The same evaluator performed all evaluations for a subject during the study.

### **5.3.2 Study Subject Assessments - Quantitative**

The study Subjects undertook multiple assessments to report their self-perceived severity of AV in general. These assessments were done at baseline encounter to document the perception of AV severity corresponding to the time of initiation of sarecycline. They were then repeated by the Subjects at ensuing encounters at Weeks 4, 8 & 12, post-index date.

#### Patient Global Assessment (PtGA)

This is based on the global acne severity question within ASIS (Item # 9), where the question asks the Subjects to assess the severity of acne, with a response ranging from 'Clear' to 'Severe', scored on a scale of 0 to 4. See Section 8.1 for general details on questionnaire scoring and administration.

#### Patient Rating of Appearance

ASIS Item # 10 asks the Subjects to rate how their face looked because of their Acne, with a response ranging from 'Excellent' to 'Bad', scored on a scale of 0 to 4. See Section 8.1 for general details on questionnaire scoring and administration.

#### Parent/Caregiver Rating of AV Severity

Parents/caregivers of children of age 12-17yrs reported their own perceived severity of children's AV, in addition to the children providing their perceptions. This was accomplished via a single item "Overall, how is your child's acne on his/her face right now?", with the 5-point likert response scales mimicking the Item # 9 in ASIS. This was scored in the same way as the corresponding ASIS item.

### **5.3.3 Study Subject Photographic Assessments**

Site Investigator from one study site took photographs of facial acne of all of their recruited patients at baseline encounter and at Week 12, during the in-person visits. This photographic data is used to document and depict the changes in acne severity that may be associated with sarecycline treatment in the study.

### **5.3.4 Study Subject Assessments - Qualitative**

Subjects from the study sites that undertook photography tasks were also asked to record a 1-3 minute audio (using the Mobile App) narrating their perceptions of treatment benefits associated with the sarecycline, at the end of their study participation or at Week 12, whichever occurred earlier. This qualitative data is used to ascertain attributes that study Subjects associate with sarecycline treatment in an un-prompted manner.

## **5.4 Additional Subject Assessments**

### Concern about Antibiotics and Antibiotic Resistance

Parents/caregivers and adult patients were asked about their concerns about (themselves or their child) using antibiotics, or concerns about antibiotic resistance, with a 5-point likert response scale of 'not at all' to 'extremely'. These questions were assessed at baseline.

### Parent/Caregiver Worries about Acne

The parents/caregivers of pediatric patients with AV were asked - how worried they are about their child's acne, with a response option of 'not at all' to 'extremely', and how concerned they are about their child's ability to accomplish future goals and reach full potential due to acne, with a 5-point likert response scale of 'not at all' to 'extremely'. These questions were asked at baseline and Week 12.

### Understanding of Acne-related Concerns

Pediatric patients (of age 12-17) were asked whether their parents understand their acne-related concerns, and correspondingly, the parents/caregivers were asked whether they understand their

child's acne-related concerns. This pair of questions have a response item on a 5-point likert scale of 'not at all' to 'very much'. These questions were asked at baseline and Week 12.

## 5.5 Compliance to Treatment

Compliance with the assigned treatment regimen was assessed by comparing the number of tablets expected to be used, based on the total number of treatment days, with the actual number used (expressed as a percentage of used/expected) at each encounter. The actual consumption/use of study tablets was evaluated by assessing the left-over pills/tablets in the medication bottles returned to sites/investigators by the Subjects.

## 5.6 Safety Assessments

### 5.6.1 *Definition of Adverse Events & Adverse Drug Reactions*

An AE is any untoward medical occurrence in a patient administered a pharmaceutical product which does not necessarily have a causal relationship with this treatment. An AE can therefore be any unfavorable and unintended sign, symptom, or disease temporally associated with the use of a medicinal product, whether or not related to the medicinal product.

The Site Investigators used the following terms to assess the severity of each AE:

- Mild: Awareness of symptoms or signs, but easily tolerated (acceptable).
- Moderate: Enough discomfort to interfere with usual activity (disturbing).
- Severe: Interferes significantly with ability to do work or usual activity (unacceptable).

A Serious Adverse Event (SAE) is any experience that suggests a significant hazard, contraindication, side effect or precaution. With respect to human clinical experience, this includes any event which:

- results in death,
- is life-threatening,

- requires inpatient hospitalization\* or prolongation of hospitalization, unless hospitalization is for:
  - routine treatment or monitoring of the studied indication, not associated with any deterioration in condition.
  - elective or pre-planned treatment for a pre-existing condition that is unrelated to the indication under study and has not worsened since the start of study drug.
  - treatment on an emergency outpatient basis for an event not fulfilling any of the definitions of a SAE given above and not resulting in hospital admission.
  - social reasons and respite care in the absence of any deterioration in the subject's general condition.
- results in persistent of significant disability / incapacity, or
- is a congenital anomaly / birth defect,
- is a significant or important medical event that, based on appropriate medical judgment, may jeopardize the subject or may require intervention to prevent one of the other outcomes listed above.

\* Hospitalization is defined as an overnight (in-patient) stay at the hospital or emergency room.

For all AEs (either related or not related to study medication), information about the outcome (resolved or ongoing) and the action taken with the study treatment (drug withdrawn, dose reduced, dose increased, dose not changed, not applicable) were documented.

Each AE, either serious or non-serious for which a causal relationship to sarecycline cannot be excluded, was considered as an ADR. An ADR is an injury caused by taking medication. ADRs may occur following a single dose or prolonged administration of a medicinal product or result from the combination of two or more medicinal products.

The determination of whether an AE is related to study treatment (sarecycline) was based on information regarding the degree to which the study treatment had caused or contributed to the event and will be categorized per the following criteria:

- Related: There were good reasons and sufficient information (e.g. plausible time sequence, dose-response relationship, pharmacology, positive de-challenge and/or re-

challenge) to assume a causal relationship with the study medication in the sense that it is plausible, conceivable or likely.

- **Not Related:** There were good reasons and sufficient information (e.g. implausible time sequence and/or attributable to concurrent disease or other drugs) to rule out a causal relationship with the study medication.

## 6 STATISTICAL CONSIDERATIONS

### 6.1 Sample Size Considerations

No formal sample size and power calculations were undertaken. Considering the descriptive nature of the study and the feasibility of recruiting the study population, approximately 300 study Subjects from across a maximum of 40 clinical sites for the entire study has been identified as a sample to guide the planned analysis addressing the study objectives. It is expected that there will be Subject attrition during the course of the study.

### 6.2 Analysis Populations and Datasets

Statistical analysis and data tabulation will be performed using the following analysis populations unless specified otherwise:

- **Safety Population:** All patients who received at least one dose of sarecycline during the study observation period, as part of usual care. This in essence constitute all 300 Subjects recruited into the study.
- **Full Analysis Set (FAS):** All patients within the Safety Population that had at least one question answered pertaining to study primary research objective. This in essence will constitute all Subjects who completed their Week-12 survey. By definition, this would exclude all Subjects who were terminated (for any reason) at any timepoint (prior to Week-12) in the study.

In the event that the safety population and FAS differ, all safety evaluations (part of additional objectives) will be conducted among the safety population, while FAS will be used to conduct

analyses addressing rest of the study objectives, including the description of population demographics, primary and secondary objectives, and select additional (non-safety related) objectives.

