patients reporting “Quite a bit/Very” at Week-12, to compute respective P values. Continuous measures will be assessed using summary statistics; paired sample t-tests will be used to assess statistical differences for CFB evaluations, while independent sample t-tests will be used to assess statistical differences between different patient groups (for subgroup analysis) for a given measure at a particular timepoint (such as Baseline or Week-12).

Computation of statistical differences will be performed only as an exploratory step (and not for hypothesis testing), considering the descriptive nature of the study; for such exploratory evaluation, P value  $\leq 0.05$  will be considered significant. All statistical analyses will be based on all available data assuming that all missing data are uninformative and will be conducted using appropriate statistical software, such as SAS.

An interim analysis will be conducted using FAS, upon completion of 12 weeks of data collection (from both patients and clinicians) for ~200 study Subjects, using the statistical methods identical to the analyses planned for FAS-based final data analyses; the focus of the interim analyses will be the primary objective, secondary objective and select additional objectives, as outlined below; no subgroup analyses will be considered.

- FAS cohort demographics
- PROs: Antibiotic attitudes at baseline
- PROs: CFB in EPQ measures
- PROs: CFB in ASIS measures
- PROs: CFB in Patient Acne Severity and How Face Looks (with and without LOCF imputation)
- PROs: CFB in Parent/caregiver concerns about the child with Acne:
  - Understanding child's concerns
  - Concerned about child's acne
  - Concerned about child's ability to accomplish future goals
- Facial IGA and Facial IGA success (with and without LOCF imputation)
- Select comparison of patient and clinician reported measures: Acne Severity (with LOCF imputation)

- Select comparison of pediatric patient and caregiver reported measures:
  - Understanding child's concerns
  - Concerned about child's acne
  - Concerned about child's ability to accomplish future goals
- Clinician satisfaction with sarecycline
- Sarecycline treatment characteristics

The description of the individual study measures are outlined in the forthcoming sections.

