## 7 DATA TABLES

All patients who received at least one dose of sarecycline during the study observation period and had at least some data pertaining to ASIS and EPQ items (related to primary research objective) at Week 12 will be included in **Full Analysis Set (FAS)** to facilitate the planned descriptive analysis. Correspondingly, patients who completed the study survey at Week 12 will be included in FAS, since patients answering Week 12 survey will have completed all relevant PRO related questions.

Safety data analyses will be conducted among the Safety Population, that correspond to the entire study cohort that took at least one does of sarecycline. Correspondingly, all patients completing the baseline survey and took at least one dose of sarecycline, amounting to N=300 will be included in this analysis.

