## 7.2 Tables from clinician's DCF (FAS Population)

Clinician data is analyzed using the FAS dataset. In relevant instances (such as IGA and physician satisfaction evaluations), only FAS dataset with corresponding week 12 clinician data is used. All data tables in this section correspond to FAS population.

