### 7.3 Tables for comparison of patient and clinician data

For tables comparing patient and clinician data, the FAS dataset is used for analysis only in the instances patient data has corresponding clinician week 12 data. All data tables in this section pertain to FAS population.

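### The SAP's Full Analysis Set is the Week-12 survey completers, so the planned Week-12 LOCF reaches no drop-out and the only missing-data sensitivity analysis cannot speak to attrition

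*SAP*

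**What the plan says.** SAP 6.2 defines the FAS in three sentences that do not agree. The first names no visit: "All patients within the Safety Population that had at least one question answered pertaining to study primary research objective". The second equates the set with those who finished the Week-12 survey. The third is explicit: "By definition, this would exclude all Subjects who were terminated (for any reason) at any timepoint (prior to Week-12) in the study". SAP 7 restates the rule for the tables ("patients who completed the study survey at Week 12 will be included in FAS") and adds that "patients answering Week 12 survey will have completed all relevant PRO related questions". SAP 6.2 assigns the FAS to the primary and secondary objectives.

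LOCF is then planned as follows:

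- SAP 6.4: ASIS items 9 and 10 at Week 12, part of the primary endpoint.
- SAP 6.5: IGA success at Week 12, the secondary endpoint.
- SAP 6.9: the same three measures, and Weeks 4 and 8 as well.
- SAP 6.11: results as observed beside results with LOCF. The only other sensitivity item is remote versus in-person visits.
- SAP 7.5: the list of table pairs that carry this comparison.

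The preamble to SAP 7.2 adds a restriction: "In relevant instances (such as IGA and physician satisfaction evaluations), only FAS dataset with corresponding week 12 clinician data is used".

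SAP 6.1 expects attrition but gives no rate. Protocol 12.8 plans a comparison of key outcomes between completers and discontinuers, with reasons for missing data and time to drop-out. SAP 6.11 carries over none of these.

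**The concern.** LOCF at the final visit is normally there to keep subjects who left early in the analysis. Here the set in which it is applied has already removed them. Readers of the report will see IGA success and the item 9 and 10 proportions twice, once with and once without imputation, in a set called the Full Analysis Set. If the two agree, they may take that as evidence that drop-out did not matter. SAP 6.11 invites this, since it says the sensitivity analyses address robustness to missing data.

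SAP 6.3.1 assumes that missing data are uninformative. A comparison that leaves out every drop-out on both sides cannot test that assumption. Tables 7.4.2 and 7.4.7 will show how many subjects left and when, but not what their outcomes would do to the endpoint.

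**Working it through.** The plan has no power calculation, attrition rate or expected success rate to reproduce. The check is therefore a count of what LOCF can fill, followed by bounds under stated assumptions.

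**1. Week-12 values open to LOCF in the operative FAS (SAP 6.2, sentences 2 and 3, and SAP 7)**

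- Subjects terminated before Week 12: 0, at any attrition rate, because none is in the set.
- ASIS items 9 and 10 among Week-12 responders: about 0, because SAP 7 takes their PRO data as complete. An occasional skipped item is possible.
- IGA among Week-12 survey completers whose clinician form is missing: all such cases under SAP 6.5, or 0 if the SAP 7.2 restriction also governs the LOCF tables. None is a drop-out.

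Missed Week 4 and Week 8 values among completers can also be filled, but they do not enter the Week-12 endpoints.

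**2. What the pairs compare**

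The Week-12 columns of Tables 7.1.12 and 7.1.14, and Tables 7.2.4.3 and 7.2.4.7, draw on the same completers. Any difference within a pair comes from the few cases in step 1, not from attrition.

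**3. How far attrition could move the proportion**

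SAP 7 gives the Safety Population as "all patients completing the baseline survey and took at least one dose of sarecycline, amounting to N=300". Let *d* be attrition, *p* the success proportion in completers and *q* the success proportion drop-outs would have had. Then

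all-treated proportion = (1 − *d*)·*p* + *d*·*q*.

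With *q* anywhere from 0 to 1, the interval has width *d*, whatever *p* is. The values of *d* and *p* below are assumptions.

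| *d* | *p* | Completers | No drop-out a success | Every drop-out a success |
|---|---|---|---|---|
| 5% | 60% | 171/285 | 171/300 = 57% | 186/300 = 62% |
| 10% | 60% | 162/270 | 162/300 = 54% | 192/300 = 64% |
| 20% | 60% | 144/240 | 144/300 = 48% | 204/300 = 68% |
| 10% | 40% | 108/270 | 108/300 = 36% | 138/300 = 46% |
| 10% | 70% | 189/270 | 189/300 = 63% | 219/300 = 73% |

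**4. What LOCF over all 300 would give**

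Entry requires IGA 3 or 4, and success requires 0 or 1. A drop-out with only a baseline IGA is therefore carried forward as a non-success. If 0% to 20% of drop-outs are successes at their last observation (assumed), then with *p* = 60% LOCF gives 54% to 56% at 10% attrition and 48% to 52% at 20%. The planned FAS would still show 60%, apart from the few cases in step 1.

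**The case against.** **The loose first sentence could be the rule.** Read alone, it admits subjects with only a baseline answer, and LOCF would then reach drop-outs. But the next two sentences and SAP 7 say otherwise in plain terms. If the loose rule was meant, those must change. The text needs reconciling either way.

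**LOCF is not idle.** This stands. Subjects answer in the mobile app and clinicians in a separate form (Protocol 11), and SAP 6.10 expects missed clinic visits. A survey completer may lack a Week-12 IGA, and SAP 6.5 would impute it. The SAP 7.2 restriction is a general preamble and may be meant only for the non-imputed tables. A reader might infer that the with- and without-LOCF tables must match; the documents do not support that for IGA. What they support is that neither table contains a drop-out.

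**SAP 7.3 looks like a further conflict.** It keeps subjects only where "the FAS dataset is used for analysis only in the instances patient data has corresponding clinician week 12 data", while SAP 6.3.1 lists the acne-severity comparison with LOCF. That item is in the interim list, and no SAP 7.3 shell is titled as imputed, so little rests on it.

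**The exclusion is open and the study descriptive.** SAP 6.2 states the exclusion, disposition is tabulated for all 300, tests are exploratory, and Protocol 12.8 still commits to the completer comparison. All true. A completer analysis is legitimate when labelled as one. But a descriptive proportion still needs a clear denominator, and the SAP promises a robustness check that its own rules defeat.

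**LOCF is itself an untested assumption.** Also true. This is why the completer result should stand beside it.

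**Conclusion.** The point holds and should be fixed before database lock. Under the FAS as SAP 6.2 and 7 specify it, Week-12 LOCF imputes no drop-out; this follows from the definitions and needs no assumption. IGA success and the item 9 and 10 proportions are completer estimates, and the SAP's only missing-data sensitivity analysis does not inform on attrition.

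A reader might go further and infer that the completer figures overstate success. The documents do not support that. They give no attrition rate and no outcomes for drop-outs, and every interval in the table includes values above the completer figure. That LOCF counts a baseline-only drop-out as a non-success is a property of the method, not evidence about that subject.

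The non-imputed ASIS domain, EPQ and satisfaction results rest on completers in any case and are not part of this point.

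**What to change.** 1. Reconcile SAP 6.2 and 7. Label the present set Week-12 completers. For IGA success and ASIS items 9 and 10, use all dosed subjects with a baseline value of that measure, about 300 on the SAP's own count.
2. Apply the already planned Week-12 LOCF in that set. State that the SAP 7.2 restriction does not govern the LOCF IGA tables (7.2.4.4 to 7.2.4.8 and 7.5.1). Show the completer result beside each. In SAP 7.5, correct the entry that lists Tables 7.1.14 and 7.1.15 as without imputation, against their titles.
3. At the interim, define the cohort only by scheduled Week-12 date: window closed by the data cut, whatever the termination status. Do not add early terminators whose window is still open, because this over-represents drop-outs. For example (assumed numbers), 20 drop-outs among 200 subjects past their window is 10%; adding 5 early terminators from later enrolment makes it 25/205 = 12.2%.
4. Keep the non-imputed ASIS, EPQ and satisfaction tables on completers, labelled as such.
5. Restore the Protocol 12.8 completer-versus-discontinuer comparison, reasons for missing data and time to drop-out. Use the baseline, Week 4 and 8 and early-termination data; Protocol 7.6 obtains the last only where possible.

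The cost is relabelling and re-running the affected tables, including subgroup Tables 7.1.16.1, 7.1.16.2, 7.2.4.5 and 7.2.4.8 and Figures 8.3, 8.4 and 8.6. No new data are needed. The reported proportions may change and under LOCF are likely to fall, by an amount that depends on attrition: up to about 12 points (60% to 48%) at an assumed 20% attrition and 60% completer success, if no drop-out is a success.
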